### **3.6. Handling of Dropouts, Missing Data and Outliers**

#### **3.6.1. Missing Data**

A missing data point for a given study visit may be due to any of the following reasons:

- A visit occurred in the window but data were not collected or were unusable
- A visit did not occur in the window
- A subject permanently discontinued from the study before reaching the window

In general, values for missing data will not be imputed unless methods for handling missing data are specified.

For missing last dosing date of study drug, imputation rules are described in Section [4.2.1](#). The handling of missing or incomplete dates for disease diagnosis is described in Section [5.3.1](#), for death in Section [6.1](#), for new anticancer therapy in Section [6.2.1.1](#), for AE onset in Section [7.1.5.2](#), and for prior and concomitant medications in Section [7.4](#). For subjects without any pre-dose laboratory values, the baseline lab toxicity grade will be treated as Grade 0 for the summary of graded laboratory abnormalities.

#### **3.6.2. Outliers**

Outliers will be identified during the data management and data analysis process, but no sensitivity analyses will be conducted. All data will be included in the data analysis.

Addition details are provided in Section [3.7](#).

### **3.7. Data Handling Conventions and Transformations**

#### **3.7.1. Data Handling for Laboratory Data**

Laboratory data that are continuous in nature but are less than the lower limit of quantitation (LLOQ) or above the upper limit of quantitation will be imputed as follows:

- A value that is 1 unit less than the limit of quantitation will be used for calculation of descriptive statistics if the data is reported in the form of “< x” (x is considered the limit of quantitation). For example, if the values are reported as < 50 and < 5.0, then values of 49 and 4.9 will be used for calculation of summary statistics, respectively. However, for direct bilirubin, a value of “< 0.1” will be treated as 0.05 for calculation of summary statistics.
- A value that is 1 unit above the limit of quantitation will be used for calculation of descriptive statistics if the data is reported in the form of “> x” (x is considered the limit of quantitation). For example, if the values are reported as > 50 and > 5.0, then values of 51 and 5.1 will be used for calculation of summary statistics, respectively.
- The limit of quantitation will be used for calculation of descriptive statistics if the data is reported in the form of “≤ x” or “≥ x” (x is considered as the limit of quantitation).

#### **3.7.2. Data Handling for PK Data**

For PK plasma /blood concentrations and analysis of PK parameters natural logarithmic transformation will be used. Plasma concentration values that are below the limit of quantitation (BLQ) will be presented as “BLQ” in the concentration data listing. Values that are BLQ will be treated as 0 at predose time points, and one-half the value of LLOQ at postdose time points for determination of summary and order statistics.

The following conventions will be used for the presentation of summary and order statistics:

- If at least 1 subject has a concentration value of BLQ for the time point, the minimum value will be displayed as “BLQ.”
- If more than 25% of the subjects have a concentration data value of BLQ for a given time point, the minimum and Q1 values will be displayed as “BLQ.”
- If more than 50% of the subjects have a concentration data value of BLQ for a given time point, the minimum, Q1, and median values will be displayed as “BLQ.”
- If more than 75% of the subjects have a concentration data value of BLQ for a given time point, the minimum, Q1, median, and Q3 values will be displayed as “BLQ.”
- If all subjects have concentration data values of BLQ for a given time point, all order statistics (minimum, Q1, median, Q3, and maximum) and summary statistics will be displayed as “BLQ.”

PK parameters that are BLQ will be imputed as one-half LLOQ before log transformation or statistical model fitting.

### 3.8. Analysis Visit Windows

#### 3.8.1. Definition of Baseline and Study Day

Baseline for efficacy is defined as the last observation within 42 days on or prior to randomization, unless otherwise specified. In the rare cases where the screening assessments are after the randomization date but prior to the first dose of andecaliximab/placebo, the assessments will be considered as baseline.

Baseline for safety is defined as the last observation within 42 days prior to first dose of andecaliximab/placebo, unless otherwise specified.

Study Day 1 for the efficacy analysis will be defined as the day of randomization.

Study Day 1 for the safety analysis will be defined as the day for the first dose of andecaliximab/placebo.

Other study days will be derived as follows:

- Assessment Date – Study Day 1 + 1 if Assessment Date  $\geq$  Study Day 1
- Assessment Date – Study Day 1 if Assessment Date  $<$  Study Day 1

#### 3.8.2. Baseline and Analysis Windows

Subject visits might not occur on protocol-specified days. Therefore, for the purpose of analysis, observations will be assigned to analysis windows.

For post baseline parameters that will be summarized by visit, an evaluation that occurs within the visit window will be considered valid for that evaluation. The visit windows are specified in [Table 3-1](#), [Table 3-2](#), and [Table 3-3](#). The lowest and highest study days are inclusive.

**Table 3-1 Post Baseline Visit Windows for Chemistry, Hematology and Vital Signs**

Analysis Visit	Relative Day	Lowest Day (inclusive)	Highest Day (inclusive)
Week 2	15	1 (after first dose)	21
Week 4	29	22	35
Week 6	43	36	49
Week X=8, 10, ...	$7 \cdot X + 1$	$7X - 6$	$7 \cdot X + 7$

**Table 3-2 Post Baseline Visit Windows for ECG, QoL and Urinalysis**

Analysis Visit	Relative Day	Lowest Day (inclusive)	Highest Day (inclusive)
Week 4	29	1 (after first dose)	43
Week 8	57	44	71
Week 12	85	72	99
Week X=16, 20, ...	$7*x+1$	$7x-12$	$7*x + 15$

**Table 3-3 Post Baseline Visit Windows for Tumor Assessment**

Analysis Visit	Relative Day	Lowest Day (inclusive)	Highest Day (inclusive)
Week 8	57	2	85
Week 16	113	86	141
Week 24	169	142	197
Week X=32, 40, ...	$7*x+1$	$7x-26$	$7*x + 29$

### 3.8.3. Selection of Data in the Event of Multiple Records in an Analysis Window

Depending on the statistical analysis method, single values may be required for each analysis window. For example, change from baseline by visit usually requires a single value per visit.

If multiple, valid, non-missing values exist in an analysis window, records will be chosen based on the following rules if a single value is needed:

For baseline:

- If there are multiple records with the same time or no time recorded on the same day, the average (arithmetic or geometric mean, as appropriate) will be used for continuous variables; the value with the lowest severity will be used for categorical variables.

For post-baseline:

- If more than one assessment occurs during the same nominal visit, select the record closest to the scheduled day for that visit.
- If there are 2 assessments that are equidistant from the scheduled day, the later record will be selected.
- The last measurement will be used if multiple measurements are taken on the same day; if the measurements occur at the same time or time cannot be determined, the average will be taken for continuous variables and the most conservative value will be taken for categorical variables.

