### **6.2.6. Electrocardiogram Assessment**

A single 12-lead electrocardiogram (ECG) will be collected at Screening, Day 1 of each cycle, at the EOT and EOS visits, per standard practice. Additional ECGs following administration of oxaliplatin will be collected at visits when oxaliplatin is administered after the infusion is completed (i.e., Days 1 and 15 of each cycle, up to a maximum of six 28-day cycles) as required per country label guidance regarding cardiac monitoring. The investigator will review all ECGs and retain the tracing with the source documents. ECGs obtained after oxaliplatin infusions must be reviewed by the investigator/sub investigator before subjects leave the clinic/infusion center.

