### 7.5.2. Corrected QT Intervals

The QT interval (measured in millisecond [msec]) is a measure of the time between the start of the Q wave and the end of the T wave in the heart's electrical cycle. The QT interval represents electrical depolarization and repolarization of the ventricles. The QT interval is affected by heart rate and a number of methods have been proposed to correct QT for heart rate.

Corrected QT (QTc) intervals will be derived using Fridericia's correction (QTcF) as follows:

$$QTcF = \frac{QT}{\sqrt[3]{RR}}$$

where QT is measured in msec; RR = 60/Heart Rate (beats per min [bpm]) and is measured in seconds

The maximum postdose QTcF interval values obtained during the study will be summarized within the following categories:

- > 450 msec
- > 480 msec
- > 500 msec

The maximum postdose change in QTcF interval values obtained during the study will also be summarized within the following categories:

- > 30 msec
- > 60 msec

QTcF and uncorrected QT values at each visit and change from baseline at each visit will be summarized by treatment arm using descriptive statistics.

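### Where a post-oxaliplatin ECG is required, the SAP's same-day rule feeds it into the by-visit QTcF change at nominal Weeks 4 to 20, so the sampling time changes when oxaliplatin ends

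*SAP*

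**What the plan says.** Protocol 6.2.6 sets two kinds of ECG. The routine one is described so: "A single 12-lead electrocardiogram (ECG) will be collected at Screening, Day 1 of each cycle, at the EOT and EOS visits, per standard practice". The other is conditional: "Additional ECGs following administration of oxaliplatin will be collected at visits when oxaliplatin is administered after the infusion is completed". The second kind applies to Days 1 and 15, for at most six cycles, and only as far as the country's label guidance on cardiac monitoring calls for it. Protocol 5.3 ends oxaliplatin after six cycles.

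The SAP gives ECGs one record per four-week window, in the table titled "Post Baseline Visit Windows for ECG, QoL and Urinalysis" (Table 3-2). It has no separate time points before and after infusion. SAP 3.8.3 then tells the analyst to "select the record closest to the scheduled day for that visit", to take the later of two equidistant records, and for same-day records: "The last measurement will be used if multiple measurements are taken on the same day". There is a fallback: "if the measurements occur at the same time or time cannot be determined, the average will be taken for continuous variables".

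The affected output is in SAP 7.5.2: "QTcF and uncorrected QT values at each visit and change from baseline at each visit will be summarized by treatment arm". SAP 7.5.3 does the same for ventricular rate, PR, RR and QRS. The safety baseline (SAP 3.8.1) is the last value before the first dose of andecaliximab/placebo.

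**The concern.** Where the label requires the extra tracing, a Day 1 visit in Cycles 1 to 6 yields two planned ECGs, and the later one is the one taken after oxaliplatin. A rule that keeps the last record of the day therefore selects it. After oxaliplatin ends, only the routine tracing remains, and the same table row type then describes a different sampling time.

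SAP 7.5 says the ECG analysis is meant to find meaningful QT changes. The protocol itself treats oxaliplatin as relevant to QT: Section 5.3.1 names it among the drugs to stop on marked prolongation, and Section 5.4 asks for care with QTc-lengthening drugs while it is given. A by-visit series in which proximity to the infusion changes partway cannot separate a change over time from a change in when the ECG was taken.

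**Working it through.** No sample size, power or alpha is involved. The check applies the SAP selection rules to the protocol's ECG schedule.

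**Inputs.** Routine and post-oxaliplatin schedule: Protocol 6.2.6. Safety Study Day 1 is the day of first dose: SAP 3.8.1. Windows: SAP Table 3-2, with targets Day 29, 57, 85 and then 7X + 1, and windows from 7X − 12 to 7X + 15 from Week 16. Selection: SAP 3.8.3.

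**Step 1, matching cycles to windows.** Day 1 of Cycle k falls on study day 28(k − 1) + 1, and the target for Week X is 7X + 1. These are equal when X = 4(k − 1). Cycles 2 to 6 are therefore Weeks 4, 8, 12, 16 and 20, and Cycle 7 is Week 24. The Table 3-2 targets are reproduced exactly.

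**Step 2, nominal schedule, extra ECG required, times recorded.**

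| Week | Target (window) | ECGs in window | Selected |
|---|---|---|---|
| 4 | 29 (1–43) | 5 | Cycle 2 Day 1, post-oxaliplatin |
| 8 | 57 (44–71) | 3 | Cycle 3 Day 1, post-oxaliplatin |
| 12 | 85 (72–99) | 3 | Cycle 4 Day 1, post-oxaliplatin |
| 16 | 113 (100–127) | 3 | Cycle 5 Day 1, post-oxaliplatin |
| 20 | 141 (128–155) | 3 | Cycle 6 Day 1, post-oxaliplatin |
| 24 | 169 (156–183) | 1 | Cycle 7 Day 1, routine only |

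Cycle 6 Day 15 is Day 155, the last day of the Week 20 window, so it does not reach Week 24.

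**Step 3, how many tracings enter.** Six cycles × 2 infusions = 12 post-oxaliplatin tracings at most. Five are selected. The other 12 − 5 = 7 (Cycle 1 Day 1 and six Day 15 visits) are not.

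**Step 4, extra ECG not required.** The single Day 1 ECG is selected at every week and the timing does not change.

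**Step 5, tied or unknown clock times.** The rule averages the two Day 1 tracings. That blends the two sampling times instead of choosing one.

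**Step 6, departures from the nominal schedule.**
- All cycles from Cycle 3 start 7 days late: Cycle 6 Day 15 falls on Day 162 and Cycle 7 Day 1 on Day 176. Each is 7 days from Day 169, the later one is taken, and the change stays at Week 24.
- All start 8 days late: these become Days 163 and 177, at distances 6 and 8. The Cycle 6 Day 15 post-oxaliplatin tracing is selected at Week 24 and the change moves to Week 28. The same holds at the longer delays tested, 14, 15, 21 and 28 days; at 28 days the Week 24 record is Cycle 6 Day 1, post-oxaliplatin.
- Cycle 2 Day 1 ECGs missing: Cycle 1 Day 15 (Day 15) and Cycle 2 Day 15 (Day 43) are both 14 days from Day 29. The later, a Day 15 post-oxaliplatin tracing, fills Week 4.
- Oxaliplatin stopped early: the change comes earlier for that subject.

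**The case against.** The strongest reply has four parts.

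First, SAP 3.8.3 applies only where a single value is needed. The laboratory and vital-sign sections cite it, while SAP 7.5 does not. SAP 7.5 also says investigator ECG assessments are summarized at each scheduled and unscheduled time point. This has some force, but that sentence is about investigator assessments, not the QTcF tables. Table 3-2 names ECG, and 3.8.3 gives by-visit change from baseline as its example of a single value being needed. Nothing in 7.5.2 or 7.5.3 overrides it, so 3.8.3 is the natural default.

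Second, the extent depends on labels that are not in the documents. This stands. If none of the 16 countries in SAP Appendix 2 requires the extra ECG, there is no problem. If all do, there is no mixing across countries, though the timing still changes when oxaliplatin stops. If only some do, Weeks 4 to 20 also mix tracings by country.

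Third, the main QT signal is covered elsewhere. This stands too: the maximum postdose QTcF and maximum-change categories in SAP 7.5.2 do not depend on the by-visit selection and can include every post-oxaliplatin tracing. ECG results are listed by subject as well, and comparing a post-dose value with a pre-dose baseline is not in itself an error. The difficulty is that the by-visit series does not do so consistently.

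Fourth, Protocol 6.2.6 does not say that the routine Day 1 ECG is taken before dosing. From about Week 24 the selected tracing is certainly not post-oxaliplatin, but calling it pre-dose would be an inference.

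A reader might go further and infer that the between-arm QTcF comparison is biased. The documents do not support that: both arms share the schedule, the rule and the blinding, and nothing in them indicates that oxaliplatin would be stopped at different rates. Nor do they support a fixed step at Week 24 for everyone, or the view that Cycle 1 and Day 15 tracings can never enter; the departures worked through above contradict both.

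**Conclusion.** The point holds as a minor one. As written, the SAP rule, and not a gap in it, places post-infusion tracings in the by-visit QTcF, QT and other interval changes at nominal Weeks 4 to 20, then tracings without oxaliplatin from about Week 24. This rests on four conditions: the label requires the extra ECG, clock times are recorded, visits run close to schedule, and 3.8.3 governs the ECG tables. Where times are tied or unknown, the value is an average of the two tracings. The change in timing comes later for subjects with delays of about 8 days or more and earlier for those who stop oxaliplatin early, so across subjects it is spread out and not a single sharp step.

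What is affected is the interpretation of change from baseline over time in descriptive tables; SAP 7.5 plans no formal ECG testing. The documents give no basis for stating a QTcF shift in milliseconds, and none is claimed.

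**What to change.** In SAP 3.8.3 and in 7.5.2 and 7.5.3, define the routine Day 1 ECG and the post-oxaliplatin ECG as separate time points. Use the routine Day 1 ECG for by-visit values and change from baseline. Tabulate the post-oxaliplatin ECGs (Days 1 and 15, Cycles 1 to 6, where collected) separately by arm. Add a cross-reference to 3.8.3 in 7.5 so that the governing rule is explicit, and state how the routine Day 1 ECG is identified when clock times are tied or missing.

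The cost is SAP wording and one extra descriptive table. No new data are needed, and the efficacy analyses and the alpha allocation are untouched.

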## 4. SUBJECT DISPOSITION

### 4.1. Subject Enrollment and Disposition

A summary of subject enrollment will be provided by treatment arm and overall. The summary will present the number and percentage of subjects enrolled. For each column, the denominator for the percentage calculation will be the total number of subjects enrolled for that column.

A similar enrollment table will be provided by each stratum in the stratified randomization. The denominator for the percentage of subjects in the stratum will be the total number of enrolled subjects within that stratum. If there are discrepancies in the value used for stratification assignment between the IWRS/IVRS and the clinical database, the value collected in the clinical database will be used for the summary. A listing of subjects with discrepancies in the value used for stratification assignment between the IWRS and the clinical database at the time of data finalization will be provided.

The randomization schedule used for the study will be provided as an appendix to the clinical study report (CSR)

A summary of subject disposition will be provided by treatment group in the ITT analysis set. The following categories will be included:

- Screened
- Randomized
- Treated with andecaliximab/placebo
- Discontinued all treatment drugs
- Discontinued all chemotherapy components
- Andecaliximab/placebo + mFOLFOX6 (all components) ongoing
- Andecaliximab/placebo + any chemo ongoing
- Andecaliximab/placebo ongoing
- Andecaliximab/placebo discontinued
  - Reasons for discontinuation
- Treated with mFOLFOX6
  - 5-FU bolus ongoing
  - 5-FU bolus discontinued
    - Reasons for discontinuation of 5-FU bolus

- 5-FU infusion ongoing
- 5-FU infusion discontinued
  - Reasons for discontinuation of 5-FU infusion
- Oxaliplatin ongoing
- Oxaliplatin discontinued
  - Reasons for discontinuation of oxaliplatin
- Leucovorin ongoing
- Leucovorin discontinued
  - Reasons for discontinuation of leucovorin
- Ongoing in lesion assessment
- Discontinued lesion assessment
  - Reasons for lesion assessment discontinuation
- Ongoing in study (including long term OS follow up)
- Completed study (including long term OS follow up)
- Discontinued study (including long term OS follow up)
  - Did not enter long term OS follow up
    - Reasons
  - Reasons for discontinuing long term OS follow up

The denominator for the percentage calculation will be the total number of subjects in the ITT Analysis Set corresponding to that column. In addition, the total number of subjects who were randomized and the number of subjects in each of the disposition categories listed above will be depicted using a flowchart.

The following by-subject listings will be provided by subject identification (ID) number in ascending order to support the above summary tables:

- Reasons for discontinuing study treatment, lesion assessment, or study.
- Reasons for screen failure (will be provided by screening ID number in ascending order)

## 4.2. Extent of Exposure

Extent of exposure to study drug will be examined by assessing the total duration of exposure to study drug, total number of doses, and the level of adherence to the study drug specified in the protocol.

### 4.2.1. Exposure to Andecaliximab/Placebo

A listing of andecaliximab/placebo administration will be provided by subject ID number (in ascending order) and visit (in chronological order), including dosing date/time, planned dosage, actual dosage administered, infusion outcome and reason for dose reduction (if applicable). Exposure to andecaliximab/placebo will be summarized by treatment arm for the safety analysis set.

#### 4.2.1.1. Duration of Exposure

Duration of exposure to andecaliximab/placebo will be summarized using descriptive statistics (N, mean, standard deviation [StD], median, minimum and maximum). Duration of exposure to study drug will be defined as (last dose end date – first dose start date + 14), regardless of temporary interruptions in study drug administration, and will be expressed in weeks using up to 1 decimal place (eg, 4.5 weeks).

If the last study drug dosing end date is missing, the last study drug start date will be used.

#### 4.2.1.2. Number of Doses

The number of doses subjects were exposed to study drug will be summarized using descriptive statistics, as well as the number and percentage of subjects exposed to a given cycle category. A subject is said to have received a dose of andecaliximab/placebo if he/she received any of the planned dose of andecaliximab/placebo.

#### 4.2.1.3. Average Dose

The average dose in mg, which is defined as (total actual dose amount received in mg) / (number of doses given), will be summarized using descriptive statistics.

#### 4.2.1.4. On-Treatment Adherence

The level of on-treatment adherence to the study drug regimen will be determined by the total amount of study drug administered relative to the total amount of study drug expected to be administered during a subject's actual on-treatment period based on the study drug regimen. Investigator-prescribed interruption and dose reductions as specified in the protocol will be taken into account.

The level of on-treatment adherence will be expressed as a percentage using the following formula:

$$\text{On-Treatment Adherence (\%)} = \left( \frac{\text{Total Amount of Study Drug Administered}}{\text{Study Drug Expected to be Administered on Treatment}} \right) \times 100$$

Descriptive statistics for the level of on-treatment adherence with the number and percentage of subjects belonging to adherence categories (eg, < 75%, ≥ 75 to < 90%, ≥ 90%) will be provided by treatment group for the Safety Analysis Set. No formal statistical testing is planned.

#### **4.2.2. Exposure to mFOLFOX6**

Exposure to individual components of mFOLFOX6 will be listed and summarized in a similar manner as for andecaliximab/placebo. mFOLFOX6 received prior to study enrollment and after the start of other anti-cancer therapy at study completion/discontinuation will not be included.

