**Table 5-1. Dose Reduction Levelsa for mFOLFOX6**

Drug	Dose Level		
	Starting Dose	-1	-2 b
Oxaliplatin	85 mg/m 	65 mg/m 	50 mg/m 
5-FU bolus	400 mg/m 	OMIT	OMIT
5-FU continuous infusion over 46-48 hours	2400 mg/m 	1900 mg/m 	1500 mg/m 
dl-Leucovorin/l-Leucovorin c	400/200 mg/m 	100%	100%

- a If an AE is believed likely to be due to 1 drug, it is permissible to decrease dose of that drug only.
- b Further dose levels (-3, -4, etc.) will be 20% dose reductions from the previous level for oxaliplatin and 5-FU continuous infusion. In addition, the bolus dose of 5-FU will continue to be omitted, and the leucovorin dose will remain unadjusted (100%).
- c Dosing of leucovorin will remain fixed at 100% of recommended dose.

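### The SAP summarizes mFOLFOX6 with measures built for a flat-dose antibody, so chemotherapy dose intensity by arm is not directly reported

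*SAP*

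**What the plan says.** SAP section 4.2 examines exposure through "total duration of exposure to study drug, total number of doses, and the level of adherence to the study drug specified in the protocol". The detailed definitions in 4.2.1 are written for andecaliximab/placebo:

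- Duration (4.2.1.1) runs from first to last dose plus 14 days, "regardless of temporary interruptions in study drug administration".
- Number of doses (4.2.1.2) counts any partly given dose as a dose.
- Average dose (4.2.1.3) is total mg divided by the count of doses actually given.
- On-treatment adherence (4.2.1.4) is the amount given over the amount expected while on treatment, with this qualification: "Investigator-prescribed interruption and dose reductions as specified in the protocol will be taken into account".

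Section 4.2.2 then carries these over: "Exposure to individual components of mFOLFOX6 will be listed and summarized in a similar manner as for andecaliximab/placebo".

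The two treatments are dosed differently. Under Protocol 5.3 and 5.3.1.1 the antibody is a flat 800 mg and resumes at its assigned dose after toxicity. mFOLFOX6 is dosed in mg/m². Table 5-1 sets reduced levels, omits the 5-FU bolus from level −1, and leaves the scale open-ended: "Further dose levels (-3, -4, etc.) will be 20% dose reductions from the previous level for oxaliplatin and 5-FU continuous infusion". Section 5.3.1.2 also lets sites follow institutional practice for reductions.

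**The concern.** In an add-on trial, a reader of the OS result will ask whether both arms received the same backbone. If the antibody added toxicity and chemotherapy were cut or delayed more in that arm, the exposure tables are where this should be visible.

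The measures suit a flat dose with no reductions. Applied to mFOLFOX6, average mg has no time term and no body-size term, and duration passes over delays. Adherence may or may not forgive permitted reductions and holds, depending on how one sentence is read. No per-subject measure in either document expresses what was given, per unit time, relative to what was planned.

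**Working it through.** The documents state no dose-intensity figure to reproduce, so the check applies the SAP 4.2.1 definitions to hypothetical courses.

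**Inputs.** Oxaliplatin starts at 85 mg/m² every 2 weeks, 12 infusions over 6 cycles; level −1 is 65 mg/m² (Protocol 5.3, Table 5-1). The 5-FU bolus starts at 400 mg/m² and is omitted at level −1. Duration is (last dose − first dose + 14 days)/7 weeks (SAP 4.2.1.1). Body surface area (BSA) is assumed to be 1.8 m².

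**Formula.** Relative dose intensity (RDI) = (cumulative mg/m² ÷ weeks) ÷ (85 ÷ 2).

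**1. Four oxaliplatin courses, each with 12 doses given**

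| Course | Weeks | Average mg | RDI | Adherence, expected amount fixed | Adherence, expected amount lowered |
|---|---|---|---|---|---|
| Full dose, on time | 24 | 153 | 100% | 100% | 100% |
| Full dose, each dose 1 week late | 35 | 153 | 68.6% | 68.6% | 100% |
| Level −1 from dose 5, on time | 24 | 129 | 84.3% | 84.3% | 100% |
| Level −1 from dose 5, 1-week delays from dose 6 | 31 | 129 | 65.3% | 65.3% | 100% |

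Row 2: eleven 3-week intervals plus 2 weeks = 35 weeks; 12 × 85/35 = 29.1 mg/m² per week; 29.1/42.5 = 24/35 = 68.6%. Average dose is 85 × 1.8 = 153 mg, as in row 1.

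Row 3: 4 × 85 + 8 × 65 = 860 mg/m²; 860/12 × 1.8 = 129 mg; 860/(12 × 85) = 84.3%.

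Row 4: seven extra weeks; (860/31)/42.5 = 65.3%.

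Average mg therefore detects reductions but not delays. Adherence either equals RDI or is 100% throughout, depending on the reading of 4.2.1.4.

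**2. Widely spaced doses.** Six full doses every 4 weeks give a SAP duration of (140 + 14)/7 = 22 weeks, in which 11 doses would be planned. RDI = 6/11 = 54.5%, with average dose still 100%.

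**3. Omitted 5-FU boluses.** Four boluses at 400 × 1.8 = 720 mg, then omission while the infusion continues to 12 doses, leave average dose at 720 mg (100%), although 4/12 = 33% was delivered. If the on-treatment period is taken per component it ends with the fourth bolus, and adherence is 100% on either reading. An RDI using weeks on the bolus also hides the loss: (4 × 400/8)/(400/2) = 100%. Using the 24 weeks on infusion gives (1600/24)/200 = 33%.

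**4. Body size.** For individuals, 85 mg/m² at 1.5 m² and 65 mg/m² at 1.96 m² are both about 127.5 mg. Between arms, assume a BSA SD of 0.15–0.25 m², a mean of 1.6–1.8 m² and 215 per arm. The 95% half-width for the difference in mean mg due to BSA alone is 1.96 × 85 × SD × √(2/215) = 2.4–4.0 mg, or 1.6–3.0% of full dose.

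**The case against.** A reader might infer that the SAP cannot show whether chemotherapy delivery differed by arm. The documents do not support that.

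- **Number of doses is summarized for each component.** Six doses rather than 12, or four boluses rather than 12, would show there. With duration it carries the delay signal too: 12 doses in 24 versus 35 weeks. This stands. The limit is that the two are summarized separately, and both also vary with time to progression, so their marginal summaries do not give per-subject intensity.
- **The feared mechanism is partly tabulated.** SAP 7.1.6.1 summarizes, by treatment group, treatment-emergent adverse events leading to modification or interruption, and to discontinuation, of 5-FU bolus, 5-FU infusion and oxaliplatin. Section 4.1 gives discontinuation reasons by component. This also stands, but these tables count subjects. They do not give the depth of a reduction or the length of a delay.
- **The adherence wording may be harmless.** It is tempting to say that adherence forgives reductions and interruptions. That is arguably the more natural reading, since the numerator already reflects what was given, but the text does not say so. On the other reading, adherence equals RDI in all four courses.
- **Randomization averages body size.** Two people of different BSA can look equally dosed in mg, but arm means are affected little. The objection largely stands. If every subject in an arm followed the row 3 course, the arm mean would fall by 153 − 129 = 24 mg, against BSA noise of 2.4–4.0 mg.
- **Similar is not identical.** Section 4.2.2 does not forbid scaling by BSA. It does not specify it either.

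**Conclusion.** The gap is real and modest. SAP 4.2.2 defines no chemotherapy dose-intensity measure, and 4.2.1.4 leaves the expected amount open, so equality of backbone delivery between arms can be inferred only indirectly. In the courses above, average dose stays at 100% while intensity is 68.6%, 54.5% or, for the bolus, 33%; adherence for one and the same course could be 65.3% or 100%. These are illustrations under an assumed BSA and assumed courses, not forecasts of what happened in the trial.

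It would be wrong to go on to say that the primary analysis is compromised. These are descriptive Safety Analysis Set summaries, and the ITT test of OS, its alpha and its power do not depend on them. Nor would an intensity table by itself separate a drug effect from under-dosing, because dose intensity arises after randomization. It would give the reader the by-arm description needed to judge that question. Dose amounts, height and visit weight are already collected, so this is a cheap improvement worth making before the tables are programmed.

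**What to change.** In SAP 4.2.2, replace the reference to the antibody measures with the following, for each mFOLFOX6 component and by arm:

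1. Average and cumulative dose in mg/m², using one named BSA formula with recorded height and that visit's weight. Mosteller is the natural choice, as Protocol 6.2.4 prefers it while allowing local formulas.
2. Relative dose intensity = (cumulative mg/m² per week) ÷ (protocol starting dose per 2 weeks, expressed per week), with the expected amount not lowered for permitted reductions, delays or omissions.
3. Weeks on 5-FU infusion as the time base for the 5-FU bolus, so that omission is visible. For oxaliplatin, limit the time base to the planned 6-cycle phase plus delays, so that its planned stop is not counted as under-dosing.
4. Categories <75%, 75 to <90% and ≥90%, matching those given as examples in 4.2.1.4.

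In 4.2.1.4, state whether permitted interruptions and reductions lower the expected amount. Keep the mg measures for the antibody.

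The cost is SAP wording, one derived dataset and one or two extra tables. Where a site dosed with a different BSA formula, small departures from 100% will appear that are not true dose changes; a table footnote should say so.
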